5.2 Patient Inclusion Criteria

To be included in the study, a patient must meet the following criteria:

1. The patient has a diagnosis of AML according to WHO criteria.
2. The patient received any induction chemotherapy regimen and may have received post-remission consolidation therapy prior to screening.
3. The patient achieved a first or second CR or CRi. For patients without evidence of MRD in CR/CRi, CR (or CRi) must have been initially identified within 12 months prior to screening.

OR

The patient has achieved first or second CR or CRI with evidence of MRD at least 6 months post stem cell transplant without evidence of acute or chronic graft-versus-host disease post-transplant and has not received immunosuppressant therapy for at least 14 days prior to SL-401 therapy.

4. The patient has adverse risk disease or AML for which there is otherwise a substantial risk of relapse, which includes but is not limited to: adverse karyotype, FLT3 internal tandem duplication (ITD) mutation, history of antecedent hematologic disorder (AHD), therapy-related AML, history of requiring more than 1 cycle of intensive induction chemotherapy to achieve first remission, and/or presence of persistent MRD (detected by cytogenetics, molecular markers, or flow cytometry) at any point after the initial induction cycle. (A more comprehensive listing of karyotypes and mutations indicative of high-risk AML is provided as an appendix to the protocol [Section [15.3](#) Appendix C]).
5. For patients enrolling in Stage 2, the bone marrow evaluation determined locally within the previous 6 months indicates the presence of MRD. (A more comprehensive listing of methodologies for evaluation of MRD is provided as an appendix to the protocol [Section [15.4](#) Appendix D]).
6. The patient is not considered to be an immediate candidate for allogeneic stem cell transplant as determined by the investigator.
7. The patient is ≥ 18 years old.
8. The patient has an Eastern Cooperative Oncology Group (ECOG) performance status (PS) of 0-2.
9. The patient has adequate baseline organ function, including cardiac, renal, and hepatic function:
 - Left ventricular ejection fraction (LVEF) \geq institutional lower limit of normal as measured by multigated acquisition scan (MUGA) scan or 2-dimensional (2-D) echocardiogram (ECHO) within 28 days prior to start of therapy and no clinically significant abnormalities on a 12-lead electrocardiogram (ECG)
 - Serum creatinine ≤ 1.5 mg/dL

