6.2.2 Stage 2: Expansion

During Stage 2, up to 20 additional patients with evidence of MRD as determined locally will be treated at the MTD or maximum tested dose at which multiple DLTs are not observed (identified in Stage 1) so that up to 15 patients with evidence of MRD as determined centrally are evaluable for safety and response at this dose. For inclusion in the study, all patients treated in the expansion phase should have MRD in bone marrow, as determined locally, via at least one of the following modalities: multi-parametric flow cytometry, cytogenetic evaluation, FISH, real-time PCR, or next-generation gene sequencing. It is anticipated that at approximately 50% of patients evaluated with AML in first remission (CR or CRi) will have evidence of MRD.

6.2.3 Tumor Assessments during Stages 1 and 2

All patients must have a baseline (pre-treatment) bone marrow aspirate (+ biopsy) and peripheral blood sample within 14 days prior to the first administration of SL-401. Subsequent assessments will be performed on the following schedules until, in the judgment of the Investigator, there is evidence of relapsed or progressive disease:

- Bone marrow aspirates (+ biopsy) and peripheral blood samples 28 (\pm 7) days after the start of Cycles 2, 4 and 6, then every 3 months (\pm 1 month) until Month 12. No repeat bone marrow is necessary if non-response or progressive disease can be unequivocally diagnosed from peripheral blood tests.
- If the Cycle 2 (Day 28 [\pm 7]) bone marrow examination is empty (i.e., hypocellular) or inadequate, a bone marrow examination should be repeated in 14 (\pm 7) days to document response. If additional time is required to complete the repeat examination, consult with the Medical Monitor.
- Bone marrow will be assessed for morphologic evidence of AML recurrence, and flow cytometric and other cytogenetic/molecular assessments, including evaluation of MRD.
- CD123 is to be assessed in all bone marrow samples (and, if applicable, tissue samples) by flow cytometry (i.e., CD123 should be added to the panel of markers assessed by flow cytometry of bone marrow aspirates) and immunohistochemistry and the results recorded and captured in the electronic case report form (eCRF). (The Cycle 2, 4, and 6, Day 28 [\pm 7 days] peripheral blood and bone marrow assessment should occur on Day 28 [\pm 7 days] even in the setting of patients receiving SL-401 over 6-10 days [as opposed to 5 consecutive days]).

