7.6.2 Procedures and Follow-up after Treatment Discontinuation

The evaluation during which the Investigator determines that SL-401 will be discontinued should be considered the End of Treatment Evaluation; all tests and procedures for the End of Treatment Evaluation are listed in [Table 6](#). In addition, patients should be followed for a minimum of 30 days after the last infusion of SL-401 for assessment of AEs (including potential new AEs and potential change/resolution of existing AEs).

If the patient is in CR/PR at the time of discontinuation, tumor assessments should continue to be performed as described in Section [8.11](#) until, in the judgment of the Investigator, there is evidence of relapsed or progressive disease. Beyond the End of Treatment Evaluation and 30-day follow up (safety/AE assessment), it is requested that subsequent follow-up occur approximately every 90 days for ascertainment of survival status.

If the patient discontinues SL-401 treatment and also withdraws consent for collection of future information, no further evaluations should be performed and no additional data should be collected as part of the study. The Sponsor will only retain and use any data collected before withdrawal of consent.

Please consult Section [6.4](#) for recommendations concerning ongoing follow-up of patients alive with or without evidence of disease progression at the time of Study Completion/assessment of primary and critical secondary endpoints.

8 Study Procedures

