8.11 Tumor Assessments

Following determination of eligibility, locally, the following assessments must be performed centrally at baseline (after local determination of eligibility, but prior to receiving investigational treatment on study) within 14 days prior to the first administration of SL-401, and on the following schedules until, in the judgment of the Investigator, there is evidence of relapsed or progressive disease.

8.11.1 Bone Marrow and Peripheral Blood Examinations including Biological/Target/Correlative Studies by Central Laboratory

Bone marrow aspirates (+ biopsy) will be collected within 14 days prior to first administration of SL-401 and 28 (\pm 7) days after the start of Cycles 2, 4 and 6, every 3 months (\pm 1 month) thereafter through 12 months after start of SL-401, and thereafter at the discretion of the Investigator. If the Cycle 2 (Day 28 (\pm 7 day) bone marrow examination is empty (i.e., hypocellular) or inadequate, a bone marrow examination should be repeated in 14 (\pm 7) days to document response. If additional time is required to complete the repeat examination,

consult with the Medical Monitor. The Cycle 2, 4 or 6, Day 28 (\pm 7 days) bone marrow assessment should occur on Day 28 (\pm 7 days) even in the setting of patients receiving SL-401 over 6-10 days (as opposed to 5 consecutive days).

For adequate MRD assessment, it is critical that the first aspirate from each bone marrow collection: 1) consists of 2 mL of BM aspirate in its entirety; and 2) be shipped in its entirety via priority overnight to the central processing laboratory ([REDACTED], Attn: [REDACTED] [REDACTED]), as described in the Laboratory Manual. Additional bone marrow may be used for local assessment at the Investigator's discretion.

Results of bone marrow examinations will be provided to the Investigator by the central laboratory within 1 week of sample receipt.

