9.7 Survival Monitoring: Approximately Every 90 Days after End of Treatment

- Survival status and response/disease progression status (for patients in PR/CR at End of Treatment), continuing until assessments of the primary and secondary objectives are completed for all patients; survival status may be performed by telephone contact.
- Patients who undergo SCT will be followed for the occurrence of VOD as part of survival monitoring.
- A blood sample for immunogenicity studies will be collected at least 16 weeks to up to 20 weeks after the last SL-401 dose.

Table 5: Study Events Schedule for Cycle 1 (Study Day -14 to Study Day 28-35)

Tests and Observations	Study Day -14 to -4	Cycle 1					
		Study Day -1 to 0	Study Days 1-5 (Up to Study Day 10 if Infusion(s) Held)		Study Day 8±3 ⁽ⁿ⁾ , 15±3, and 21±3	Study Day 28±3 ^(o)	Study Day 35±3, Then Every 7±3 days
			SL-401 Treatment				Delayed End of Cycle for Toxicity Resolution Only if Required
Screening	Pre-treatment	Pre-Infusion	Infusion	End of Cycle ^(o)			
Informed consent form	X						
Inclusion/exclusion criteria	X						
Medical history including prior therapy, concomitant medications	X						
Concomitant Medications		X			X	X	X
ECOG performance status	X					X	X
Physical examination	X	X				X	
Pregnancy test ^(a)	X						
Vital signs and weight ^(b)	X	X	X	X		X	X
12-lead ECG ^(c)	X	X	X	X (Infusions 1, 5)		X	X
ECHO or MUGA scan ^(d)	X						
Hematology ^(e)	X	X	X		X	X	X
Serum electrolytes ^(f)	X	X	X		X	X	X
Serum albumin ^(g)	X	X	X		X	X	X
Serum chemistry ^(h)	X	X	X		X	X	X
Coagulation parameters: PT/INR, aPTT	X		X		X	X	X
Urinalysis ⁽ⁱ⁾	X		X (Infusion 1)		X	X	X
Tumor response assessment: Bone marrow aspiration + biopsy ^(j)	X						
Administration of premeds ^(k)			X				
SL-401 administration ^(l)				X			
Pharmacokinetic sampling ^(m)			X (Infusions 1, 5)	X (Infusions 1, 5)			
Immunogenicity sampling			X (Infusion 1)		X (day 15)	X	
Vision assessment	X				X (day 21)		
AE and SAE monitoring			X	X	X	X	X

a Urine or serum pregnancy test must be performed within 1 week prior to treatment in women of childbearing potential.

b Vital signs should be performed after patient is sitting for 3-5 minutes. If during dosing period, vital signs should be taken immediately prior to infusion, immediately after completion of infusion, and 30, 60, and 240 minutes post-infusion.

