- l After the follow-up visit, patients will then be followed every 90 days for survival status for at least one year following the start of SL-401. The survival follow-up may be by telephone contact. Patients who undergo SCT will be followed for the occurrence of VOD as part of long-term follow-up. A blood sample for immunogenicity studies will be collected at least 16 weeks to up to 20 weeks after the last SL-401 dose.
- m For patients who live a considerable distance from the Study Center, for whom weekly travel to the Study Center is not feasible, the Day 8, 15, and 21 (\pm 3 days) laboratory assessments (blood and urine) may be submitted to a local laboratory, although the results must be evaluated by the Study team. Concomitant medication and AE monitoring on these days will take place via telephone contact. In situations where SL-401 is not administered over 5 consecutive days (i.e., treatment delays because of AEs or other factors) and an infusion is to be administered on Day 8, all pre-infusion/infusion evaluations should be conducted, in addition to concomitant medications recorded. Upon completion of the 5th Cycle 1 infusion (Day 8, 9 or 10), the blood/urine/concomitant medication and AE assessments should be planned for Day 15, as indicated in the table.
- n The end-of-the cycle evaluations (Day 28 or thereafter) may also serve as the pre-infusion evaluations for the subsequent cycles; these do not need to be duplicated on successive days unless there is an abnormality or other clinically relevant reason for repeat evaluation.

Table 7: Time Points for Pharmacokinetic Blood Draws and ECGs

Collection Timepoint	Day			
	Cycles 1 and 3: Day 1/Infusion 1		Cycles 1 and 3: Day 5/Infusion 5	
	ECG	PK	ECG	PK
Pre-Infusion	X	X	X	X
Immediately After End of Infusion (time recorded)		X		X
15 Minutes Post-Infusion		X		X
30 Minutes Post-Infusion	X	X	X	X
45 Minutes Post-Infusion		X		X
60 Minutes Post-Infusion	X	X	X	X
90 Minutes Post-Infusion		X		X
120 Minutes Post-Infusion		X		X
180 Minutes Post-Infusion		X		X
240 Minutes Post-Infusion		X		X

10 Adverse Events and Safety Evaluation

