4.3.2. Relapse-Free Survival

Relapse-Free Survival is defined as the time from the date of first infusion of Tagraxofusp to the date of relapse (AML recurrence) or death from any cause, whichever occurred first. According to current WHO classification, a myeloblast population comprising greater than 5% of nucleated cells in the bone marrow or blood is required for diagnosis of AML relapse following CR/CRi

(if no peripheral blasts are present, then a confirmation aspirate is required ≥ 1 week subsequent to the aspirate at which $>5\%$ blasts were identified).

For patients who receive SCT, RFS will include time to progressive disease or death post-transplant. Patients who do not progress and are still alive at the time of analysis will be censored on the date of last treatment recorded prior to the analysis cut-off date. If patients start other anticancer therapies (with the exception of SCT or preparations for SCT), they will be censored at the latter of the date of last treatment with Tagraxofusp or date of last disease assessment recorded that occurred prior to the start of the new therapy.

The proportion of subjects receiving treatment who are alive and without evidence of AML recurrence will be presented. The distribution for RFS will be estimated by Kaplan-Meier methodology and the 25th percentile, median, 75th percentile, number and percentage of events and censored observations, and appropriate CIs will be presented. 6- and 12-month RFS rates will be evaluated.

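### After SL-401 stops, Protocol 7.6.2 and 9.7 continue disease assessment for patients in CR/PR without naming CRi, which contradicts 6.2.3 and 8.11 and leaves relapse follow-up for RFS open to two readings.

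*Protocol*

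**What the plan says.** Two sections limit disease follow-up by response category once treatment ends:

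- Protocol 7.6.2: "If the patient is in CR/PR at the time of discontinuation, tumor assessments should continue to be performed", on the schedule of Section 8.11.
- Protocol 9.7, on the 90-day contacts: "response/disease progression status (for patients in PR/CR at End of Treatment".

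Two sections set no such limit:

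- Protocol 6.2.3: "Subsequent assessments will be performed on the following schedules until, in the judgment of the Investigator, there is evidence of relapsed or progressive disease".
- Protocol 8.11: "on the following schedules until, in the judgment of the Investigator, there is evidence of relapsed or progressive disease". Section 8.11.1 then runs marrows every 3 months "thereafter through 12 months after start of SL-401, and thereafter at the discretion of the Investigator".

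CRi is an eligible entry state. Protocol 5.2, criterion 3, reads: "The patient achieved a first or second CR or CRi". Appendix A gives CRi its own row and notes that all patients are in CR or CRi at entry.

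The 90-day contact is described in different ways. Table 6 footnote l says "patients will then be followed every 90 days for survival status for at least one year following the start of SL-401" and allows the telephone. Section 7.6.2 likewise speaks of survival status, while 9.7 adds progression status.

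On later therapy, SAP 4.3.2 says: "If patients start other anticancer therapies (with the exception of SCT or preparations for SCT), they will be censored".

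**The concern.** RFS is a secondary objective, reported as a Kaplan-Meier curve with 6- and 12-month rates and as a direct proportion of patients alive with no known recurrence. Both need relapse to be looked for in every patient still in remission, on and off treatment.

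Read literally, 7.6.2 and 9.7 leave out one of the two states in which patients enroll. They name instead a state that hardly applies: Appendix A puts PR at 5 to 25% marrow blasts (or fewer with Auer rods), and more than 5% after CR or CRi already counts as relapse. CRi at discontinuation is foreseeable, because entry requires only a neutrophil count above 0.5 x 10^9/L and sets no platelet minimum.

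If a site stops assessing CRi patients, deaths still reach the database but relapses may not, or may be recorded late. A survivor with an unseen relapse is then counted as relapse-free. A patient who relapses unseen and then dies has the event dated to death.

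**Working it through.** **The plan's own figure.** The documents give no power or precision figure for RFS. The only sample-size figure is the Stage 2 MRD rule (at least 2 of 15; 5% versus 20%). It reproduces: alpha = 1 − 0.95^15 − 15(0.05)(0.95^14) = 0.171, and power = 1 − 0.8^15 − 15(0.2)(0.8^14) = 0.833. It has no bearing on this point.

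**The rules side by side.**

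| Section | Who continues | Until |
|---|---|---|
| 6.2.3 | all patients | relapse or progression; marrows to Month 12 |
| 8.11, 8.11.1 | all patients | the same; discretionary after Month 12 |
| 7.6.2 | CR/PR at discontinuation | relapse or progression |
| 9.7 | PR/CR at End of Treatment (progression status) | objectives assessed |
| Table 6, footnote h | all patients | Month 12 |
| Table 6, footnote l | all patients (survival status) | at least one year from start |

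Section 7.6.2 is the specific rule for patients off treatment, and it points to 8.11, which has no category limit. If 8.11 governs, the condition in 7.6.2 does nothing. If the condition has force, CRi patients fall outside it. The text does not say which applies.

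**Window exposed.** Six undelayed cycles last 6 × 28 = 168 days, about 5.5 months. About half of a 12-month RFS window lies after treatment, and more for patients who stop early.

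**Weight of one missed relapse.** SAP 3.1 reports 9 patients enrolled in Stage 2 and 18 in Stage 1. One missed relapse in a survivor moves the direct proportion by 1/9 = 11.1 points in Stage 2, or 1/27 = 3.7 points over both stages.

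**Illustration under the literal reading.** All inputs are assumptions:

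- 12-month relapse in CR patients, q: 0.30 or 0.60. These are round values taken from the 1-year rates quoted in Protocol 3.1.3 for intermediate-risk AML (below 30% without MRD, above 60% with it).
- Share in CRi at discontinuation, f: 0.1 to 0.5.
- CRi:CR relapse hazard ratio, h: 1 to 2.
- Month of discontinuation, t0: 2 or 6.
- CRi relapses after t0 are never seen, deaths are ignored, CR patients are fully followed, and unassessed patients are censored at t0, in line with Protocol 11.5.2.

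With S(t;h) = (1 − q)^(ht/12):

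- True 12-month RFS = (1 − f)S(12;1) + f S(12;h)
- Kaplan-Meier = [(1 − f)S(t0;1) + f S(t0;h)] × S(12;1)/S(t0;1)
- Direct proportion at 12 months = (1 − f)S(12;1) + f S(t0;h)

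Example with q = 0.6, f = 0.3, h = 1.5, t0 = 2:

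- S(12;1) = 0.400, S(12;1.5) = 0.253, S(2;1) = 0.858, S(2;1.5) = 0.795.
- True = 0.7(0.400) + 0.3(0.253) = 0.356.
- Kaplan-Meier = [0.7(0.858) + 0.3(0.795)] × 0.400/0.858 = 0.391.
- Direct proportion = 0.280 + 0.3(0.795) = 0.519.

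Selected results at f = 0.3:

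| q | h | t0 | True | Kaplan-Meier | Direct proportion |
|---|---|---|---|---|---|
| 0.3 | 1 | 2 | 0.700 | 0.700 | 0.773 |
| 0.3 | 1.5 | 2 | 0.666 | 0.694 | 0.764 |
| 0.3 | 2 | 6 | 0.637 | 0.666 | 0.700 |
| 0.6 | 1 | 2 | 0.400 | 0.400 | 0.538 |
| 0.6 | 1.5 | 2 | 0.356 | 0.391 | 0.519 |
| 0.6 | 2 | 6 | 0.328 | 0.356 | 0.400 |

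Over the whole grid, Kaplan-Meier is unbiased at h = 1 and 0.5 to 9 points too high at h = 1.5 to 2. The direct proportion is about 1 to 29 points too high, including at h = 1. Because deaths are ignored, the Kaplan-Meier figures leave out the further error from dating a missed relapse to death.

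**The case against.** The strongest reply is that nothing is lost. Section 7.6.2 says who continues, not who stops, and no section says that CRi patients stop. Sections 6.2.3, 8.11 and Table 6 footnote h carry marrows to Month 12 without a category limit. An End of Treatment marrow is scheduled for everyone, and 6.2.3 says patients are followed for RFS. CR may also be shorthand, since the title and 11.2 use it for remission although CRi is eligible. This stands to the extent that the defect is a contradiction and not a proven loss. It does not settle the matter: 5.1, 5.2, 6.2.2, 8.1 and 11.5.2 all write CR and CRi separately, and the condition in 7.6.2 serves no purpose if 8.11 already covers everyone. The Survival Extension Period in 6.4 would collect recurrence regardless of category, but it is optional and feeds a supplemental database after lock.

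A reader might go further on several points, and the documents do not support it:

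- **A count of affected patients.** Any CRi percentage is a guess. Applying it to all 27 enrolled also includes patients who stop because of relapse, death or withdrawn consent and have no assessment left to lose.
- **Patients whose counts fell on treatment.** No rule moves a patient from CR to CRi at discontinuation, and Appendix A lists a fall of at least 50% in platelets or granulocytes under progressive disease.
- **Informative loss.** This needs a different relapse hazard in CRi, which the documents do not give.
- **Later therapy going unrecorded.** Section 8.3 asks for medications throughout the study, and SAP 4.4.6 plans listings of subsequent treatment. What is missing is a scheduled point: 9.6 and Table 6 mark medications only to 30 days after the last infusion, and 9.7 lists none.

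**Conclusion.** The point holds as a contradiction in a follow-up rule that feeds RFS. Sections 7.6.2 and 9.7 must be reconciled with 6.2.3 and 8.11. Under the literal reading, the direct proportion would be too high whatever the relapse rate in CRi. Kaplan-Meier RFS would lose precision, and could be biased if CRi patients relapse at a different rate or a missed relapse is dated to death. The ranges above (about 1 to 29 points, and 0.5 to 9 points at hazard ratios 1.5 to 2) rest wholly on assumed inputs. The number of patients affected cannot be derived from the documents. RFS is secondary and descriptive, so the primary objectives and the Stage 2 MRD rule are untouched.

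SAP 4.3.2 also censors living, event-free patients at last treatment. That affects CR patients as well, is a separate issue, and is not cured by the change proposed here.

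**What to change.** 1. In 7.6.2 and 9.7, replace CR/PR and PR/CR with *CR or CRi (no relapse as defined in 11.5.2)*, to match 6.2.3 and 8.11.
2. Align Table 6 footnote l and the 90-day contact in 7.6.2 with 9.7, so that each contact records relapse status and its date.
3. At the same contact, record the start date of any subsequent anti-leukemia therapy, including SCT. SAP 4.3.2 needs these dates to apply its censoring rule and its exception for SCT.

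The cost is a wording change and two extra items at a contact that already takes place; 8.11 already schedules the marrows. If follow-up has closed, as the enrollment-at-lock statement in SAP 3.1 suggests, the report should give the number of patients in CRi at discontinuation with their last disease-assessment dates. It should also show the direct proportion with unassessed survivors counted both as relapse-free and as relapsed.
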